7.2. General Methodology

Descriptive statistics of continuous measures will be presented and include sample size, mean, standard deviation, median, first and third quartiles, minimum and maximum. For categorical outcomes, the number and percentage of subjects in each category will be presented. Paired t-tests will be used to compare changes in continuous measures from baseline to follow-up. All statistical analyses will be performed using SAS for Windows (version 9.4 or higher) or other widely accepted statistical or graphical software. Subject data listings and tabular or graphical presentations of results will be provided.

7.3. Handling of Missing Data and Dropouts

No imputation of missing data will be performed.

7.4. Adjustments for Multiple Comparisons

This study contains no powered endpoints or formal hypotheses, therefore adjustments for multiple comparison will not be made.

7.5. Demographic and Other Baseline Characteristics

Baseline variables will be tabulated. Categorical variables, including binary variables, will be reported by giving the number and percentage of patients in each category. Continuous variables will be reported by presenting the number of values, mean, standard deviation, median, first and third quartiles, minimum and maximum value for each. No imputation will be performed for missing data.

7.6. Treatment and Anti-hypertensive Medications Characteristics

Renal denervation treatment measures will be summarized separately for each kidney, and combined. Anti-hypertensive medication use will also be summarized at baseline and at each follow-up.

7.7. Evaluation of Objectives

7.7.1. Safety Objectives

The following safety endpoints will be evaluated:

- Major Adverse Events (MAE), defined as a composite of the following event at 1 month post-procedure (6 months for renal artery stenosis):
 - All-cause mortality
 - End-stage renal disease (ESRD)
 - Significant embolic event resulting in end-organ damage
 - Renal artery perforation requiring intervention
 - Renal artery dissection requiring intervention
 - Vascular complications
 - Hospitalization for hypertensive crisis not related to confirmed non-adherence with medications or the protocol
 - New renal artery stenosis >70%, confirmed by angiography and as determined by the angiographic core lab at 6 months follow-up
- Composite safety endpoint, defined as a composite of the following event at 3, 6 and 12-month post-procedure:
 - All-cause mortality
 - End-stage renal disease (ESRD)
 - Significant embolic event resulting in end-organ damage
 - Renal artery perforation requiring intervention
 - Renal artery dissection requiring intervention
 - Vascular complications
 - Hospitalization for hypertensive crisis not related to confirmed non-adherence with medications or the protocol

This document is electronically controlled. Printed copies are considered uncontrolled.

Confidential

- New renal artery stenosis >70%, (For the composite safety endpoint at 3 and 6 months, use RAS at 6 months, which confirmed by angiography and as determined by the angiographic core lab at 6 months follow-up. For the composite safety endpoint at 12 months use RAS available at 12 months)
- Myocardial infarction
- Stroke
- Renal artery re-intervention
- Major bleeding according to TIMI definition (i.e. intracranial hemorrhage, $\geq 5\text{g/dl}$ decrease in hemoglobin concentration a $\geq 15\%$ absolute decrease in hematocrit, or death due to bleeding within 7 days of the procedure)
- Increase in serum creatinine $>50\%$ from SV2 (not CEC adjudicated)

All the safety endpoints except "Increase in serum creatinine $>50\%$ from SV2" will be adjudicated by the Clinical Events Committee (CEC). The following algorithm will be used to evaluate the safety event rates: The denominator will include all subjects who either had a CEC adjudicated event prior to the time of interest (180 days for 6 months events, for example), or had last contact date that is beyond the lower window of the follow up (166 days for 6 month events, for example). The numerator will include all subjects who had CEC adjudicated events up to the time of interest (180 days for 6 months events, for example).

The safety endpoints will be summarized using counts and percentages, and no comparison group will be used for the safety analysis. These analyses will be performed for the ITT population defined in 7.1.3.1.

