**Table 1: Schedule of Treatments and Assessments**

Required Assessments	Screening			Procedure		Post-procedure follow up								
	SV1	2Wk	SV2	Procedure	DC	2Wk	1M	6Wk	8Wk	10Wk	3M	4M	6M	12M
Mode (O- in office, P-phone)	O	O	O			O	O	P 	P 	P 	O	O	O	O
Window (M-month, Wk-week, d-days)	--	±3 d			--	±3 d	±7 d	±3 d	±7 d	±3 d	±14 d	±7 d	±14 d	±30 d
Medical history	X													
Clinical assessment		X	X			X	X				X	X 	X 	X 
Renal denervation procedure				X										
OBP per study guidelines	X	X	X		X	X	X	X 	X 	X 	X	X	X	X
24h ABPM per study guidelines			X								X		X	X
Witnessed pill intake 													X	X
Medications prescribed 												X 		
Blood tests (Chem7) 			X		X		X				X		X	X
Serum or urine pregnancy test			X											
Drug testing			X								X			
Renal artery imaging- angiogram				X										
Renal artery imaging-DUS 													X	
Mortality assessment 						X	X	X	X	X	X	X	X	X
Medication and event review	X	X	X	X	X	X	X	X	X	X	X	X	X	X 

1: 4M follow-up is only required if 3M systolic OBP≥140 mmHg, prescribe AH medications according to **section 9.1.9** if SBP ≥ 140 mmHg

2: If medically necessary, phone contact may be replaced with office visit. OBP (per **Appendix 16.5**) to be obtained for an office visit or following alternative methods of data collection as described in **section 9.1.6**.

3: Witnessed pill intake (if subject is taking AH medications), complete after OBP measurements

4: Bicarbonate will not be measured for subjects enrolled in Europe.

5: DUS required as first line imaging modality at 6M. Repeat DUS, MRA, CT or angiogram to be used if DUS is nondiagnostic. Renal angiography must be used if repeat DUS/CTA/MRA is nondiagnostic or stenosis >60-70% is suspected. If renal imaging is not captured at the 6M follow-up visit due to extenuating circumstances, renal imaging is required at the next scheduled study visit.

6: Mortality assessment will be completed by the investigational site when a subject cannot be reached after each of the protocol required follow-up visits

7: SAE only review required at 12M visit

8: Clinical assessment of weight only

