#### 4.2.2. *Safety endpoints*

- Composite safety endpoint at 1, 3, 6, and 12 months post-procedure:  
Incidence of the following events:
  - All-cause mortality
  - End-stage renal disease (ESRD)
  - Significant embolic event resulting in end-organ damage
  - Renal artery perforation requiring intervention
  - Renal artery dissection requiring intervention
  - Vascular complications

- Hospitalization for hypertensive crisis not related to confirmed non-adherence with medications or the protocol
- New renal artery stenosis > 70%, confirmed by angiography and as determined by the angiographic core lab at 6-months follow up
- Myocardial infarction
- Stroke
- Renal artery re-intervention
- Major bleeding according to TIMI definition (i.e., intracranial hemorrhage,  $\geq 5$  g/dl decrease in hemoglobin concentration, a  $\geq 15\%$  absolute decrease in hematocrit, or death due to bleeding within seven days of the procedure)
- Increase in serum creatinine  $> 50\%$  from Screening Visit 2

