- **Renal artery imaging** will be performed at the 6-month follow-up visit to assess if a renal artery stenosis is suspected. A renal duplex ultrasound (DUS) will be obtained at 6-months follow up and submitted to the DUS Core Laboratory. If the DUS is determined to be nondiagnostic a repeat DUS, a MRA, CT or angiogram will be performed (repeat imaging is to be completed within 30 days after confirmation of non-diagnostic imaging). If evidence of a clinically significant stenosis is indicated by the DUS or MRA/CT Core Laboratory, an angiogram must be obtained and submitted to the angiographic core laboratory.
  - If renal imaging is not obtained at the 6-month follow-up visit due to extenuating circumstances, renal imaging is required at the next scheduled study visit.
- **24-hour ABPM** will be conducted at the 3, 6, and 12-month follow-up visits post-procedure according to the guidelines in **Appendix 16.5**. A repeat ABPM will be required in the event of technical issues, failure to follow ABPM guidelines or if the minimum required number of daytime and nighttime readings is not obtained. If ABPM is repeated office blood pressure and drug testing (for 3-month follow up only) must be repeated on day the ABPM is applied.
  - Initiate medication re-Introduction for subjects with systolic OBP  $\geq 140$  mmHg at 3-month follow-up visit. Starting at the 3-month follow up after clinical assessment and a valid ABPM are completed.
- **Mortality assessment** will be completed by the investigational site when a subject cannot be reached after each of the protocol required follow-up visits.
- **Drug testing** (urine/blood) to ensure medications are no longer present in the subject's system. A urine sample will be collected, preferably using the subject's first morning urine. A blood sample will be collected at the time of the visit. Drug testing samples collected for subjects that screen fail after obtaining the sample, must not be sent to the core lab for analysis.

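### The stenosis component of the safety composites is counted over subjects in contact, not subjects imaged, so a treated subject without a diagnostic renal image counts as stenosis-free

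*SAP*

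**What the plan says.** **Where stenosis enters.** SAP 7.7.1 puts stenosis above 70% in the 1-month MAE, with the qualifier "6 months for renal artery stenosis". For the later composites it says "For the composite safety endpoint at 3 and 6 months, use RAS at 6 months" and then "For the composite safety endpoint at 12 months use RAS available at 12 months". Protocol 4.2.2 defines the component as "confirmed by angiography and as determined by the angiographic core lab at 6-months follow up", although the composite it belongs to is reported at 1, 3, 6 and 12 months.

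**When imaging is done.** Protocol 9.1.6 states: "A renal duplex ultrasound (DUS) will be obtained at 6-months follow up and submitted to the DUS Core Laboratory". The footnote to Protocol Table 1 agrees ("DUS required as first line imaging modality at 6M") and adds "If renal imaging is not captured at the 6M follow-up visit due to extenuating circumstances, renal imaging is required at the next scheduled study visit". After the 6-month visit, the next scheduled visit is 12 months. Protocol Tables 2 and 4, for subjects who meet the escape criteria, mark imaging at the same single visit.

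**Who is in the denominator.** SAP 7.7.1 admits a subject who has an adjudicated event before the time of interest, "or had last contact date that is beyond the lower window of the follow up". Its worked example is 6 months: a contact floor at day 166 and an event limit at day 180. No diagnostic image is required. SAP 7.3 imputes nothing.

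**The concern.** Stenosis is found by imaging. A subject can be in contact with the site at and after 6 months and still have no diagnostic image, and the stated rule then places that subject in the denominator as a non-event. The missing image is never recognised as missing, so the no-imputation rule in SAP 7.3 does not come into play.

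This is foreseeable. In extenuating circumstances, Protocol 9.1.6 allows home, virtual and telephone visits. It lists renal imaging among the assessments that none of them can provide, and it waives deviation entry for data missed for that reason. A telephone visit therefore keeps the subject in contact without imaging.

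The SAP treats other measurements differently. Appendix IV requires at least 21 daytime and 12 night-time readings before an ABPM is analysed, and Appendices II, III, V and VI set selection windows for office pressure, ABPM, laboratory values and drug tests. Renal imaging has neither an evaluability rule nor a window.

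At stake is a safety rate that can err in one direction only, towards looking safer, and a 12-month figure that may be read as 12-month ascertainment.

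**Working it through.** **Inputs**

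- Treated subjects: about 50 (SAP section 5; Protocol section 5).
- Visit targets and protocol windows in days (SAP Appendices II and V): 30 (23-37), 90 (76-104), 180 (166-194), 360 (330-390).
- Six-month limits in SAP 7.7.1: contact floor 166, event limit 180.
- Treated subjects never diagnostically imaged, *u*: not given in the documents. Assumed 5 to 10 of 50 (10-20%), with 0 and 15 as outer cases. All 50 are assumed to be in contact beyond day 166.

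**Step 1. Reproduce the plan's figures.** Floor = target minus window half-width. For 6 months, 180 − 14 = 166, as stated. By analogy, 30 − 7 = 23, 90 − 14 = 76 and 360 − 30 = 330, which match the appendix windows.

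**Step 2. Apply the rule to an un-imaged subject.** Contact beyond day 166 puts the subject in the denominator. With no image there is no angiographic confirmation and so no event. The subject adds 1 to the denominator and 0 to the numerator.

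**Step 3. Size.** The SAP rule gives x/50 and the imaged-only rule gives x/(50 − *u*). With zero events, the exact (Clopper-Pearson) two-sided 95% upper limit is 1 − 0.025^(1/n).

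| *u* | n imaged | 1 event, SAP rule | 1 event, imaged only | 0 events, upper limit at n = 50 | 0 events, upper limit at n imaged |
|---|---|---|---|---|---|
| 0 | 50 | 2.0% | 2.0% | 7.1% | 7.1% |
| 5 | 45 | 2.0% | 2.2% | 7.1% | 7.9% |
| 10 | 40 | 2.0% | 2.5% | 7.1% | 8.8% |
| 15 | 35 | 2.0% | 2.9% | 7.1% | 10.0% |

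If un-imaged subjects carry the same risk *p* as imaged ones, the expected rate under the SAP rule is *p* × (50 − *u*)/50. With *p* = 5% and *u* = 10, that is 5% × 40/50 = 4.0%.

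**Step 4. The 1- and 3-month composites.** Both take their stenosis result from 6 months. If the floors of their own visits apply, a subject enters at day 23 or day 76. That is 166 − 23 = 143 or 166 − 76 = 90 days before the earliest in-window 6-month image, so a subject last seen on day 40 would count as stenosis-free in the 1-month MAE. If the stenosis component keeps its 6-month floor, that subject is out of the stenosis denominator. SAP 7.7.1 illustrates only the 6-month case and does not say which applies.

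**Step 5. The 12-month composite.** For a subject imaged in window at 6 months, the interval to an in-window 12-month visit runs from 330 − 194 = 136 to 390 − 166 = 224 days. No imaging is scheduled in that interval or at the 12-month visit.

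**The case against.** **Safeguards.** A non-diagnostic ultrasound leads to repeat imaging within 30 days of confirmation that it was non-diagnostic (Protocol 9.1.6). Angiography is mandatory if the repeat is also non-diagnostic (footnote to Protocol Table 1). A missed 6-month image must be made up at the next scheduled visit. Four contact attempts are required before a visit counts as missed (Protocol 9.6.2). Only subjects who never complete this sequence are miscounted, and the 10-20% has no basis in the documents. This stands, and it is why the effect is called modest.

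**Reporting.** Protocol 13.7 promises the number of subjects in each analysis so that readers can judge missing data. This does not cure the problem, because the denominator rule counts un-imaged subjects as analysed.

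**No decision depends on it.** Safety is summarised by counts and percentages, without comparator or formal hypothesis (SAP 7.4 and 7.7.1). That is correct. The confidence limits above are illustrative and are not planned output.

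**Stronger readings a reader might infer, which the documents do not support:**

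- *That the 12-month stenosis figure has no 12-month assessment at all.* Catch-up imaging is required at 12 months when the 6-month image was missed, unscheduled repeat imaging is provided for (Protocol 9.1.7), and the SAP wording can be read as cumulative. What is absent is routine 12-month imaging.
- *That the SAP definitely applies a day-23 floor to stenosis in the 1-month MAE.* SAP 7.7.1 names 6 months as the time for that component, so a day-166 floor is at least as natural a reading.
- *That stenosis is the main late vascular risk, or that branch treatment sets this technique apart.* Protocol 10.1 lists stenosis among several risks not yet quantified and does not rank them. Protocol 3.1 reports that SPYRAL HTN-OFF MED also treated branches, with on average 25.9 branch ablations in addition to 17.9 in the main arteries.

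**Conclusion.** The point holds as a gap in the analysis rule. Routine imaging happens once, the denominator does not ask whether it happened, and treated subjects in contact but never diagnostically imaged count as free of stenosis. The bias is downward.

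Its size rests on an assumed un-imaged fraction. At 10-20% of 50, one event is understated as 2.0% instead of 2.2-2.5%, and the zero-event upper limit as 7.1% instead of 7.9-8.8%. If everyone is imaged, the two rules agree. Two terms also need defining: which contact floor governs stenosis in the 1- and 3-month composites, and what the 12-month stenosis term includes. The correction is cheap and should be made, but nothing here suggests that the study's safety conclusions would be overturned.

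**What to change.** In SAP 7.7.1:

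1. Report stenosis separately. The denominator is treated subjects with diagnostic renal imaging in a stated window, for example the expanded 6-month window the SAP already uses for other measurements (days 136-270), plus 12-month catch-up for the 12-month figure. Apply the same window to positive and negative images, and list any stenosis found outside it. For this component the window must also replace the day-180 event limit, or late in-window findings would be lost from the numerator.
2. Report the numbers imaged and not imaged beside the rate.
3. Keep the planned composite. Add a sensitivity version in which un-imaged subjects with no other component event are non-evaluable, while every subject with any component event is retained, so that deaths and other early events are not dropped.
4. State that the 6-month floor applies to the stenosis component of the 1- and 3-month composites.
5. Define the 12-month stenosis term as cumulative stenosis through a stated day from 6-month, catch-up and unscheduled imaging, with a footnote that no routine 12-month imaging is done.

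No imaging is added. The cost is SAP wording and one footnoted table. The downside is a smaller denominator and a slightly less favourable rate.

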### ***9.1.8. Confirmatory Blood Draws to Assess Renal Function***

Serum creatinine values will be assessed throughout the study. A second blood draw will be required to confirm a sustained change in renal function in the event of one of the following:

- >50% increase in serum creatinine from baseline (Screening Visit 2)
- eGFR <15 mL/min/1.73m^2 using the 4 variable MDRD calculation

The additional blood draw must be taken at least 21 days from the date of the event noted above and documented on an Unscheduled Follow-up CRF. In the event the second blood draw results in the same event (e.g., >50% increase in serum creatinine from baseline), an adverse event must be reported. If the event is a continuation of an already-identified sustained elevation that did not return to <50% of baseline value, another blood draw is not necessary.

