### **13.5. Safety Endpoint Analysis**

All the safety endpoints will be adjudicated by the clinical events committee (CEC). The safety endpoints will be summarized using counts and percentages, and no comparison group will be used for the safety analysis.

These analyses will be performed for the ITT population defined in 13.2.1.

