11.5. Appendix V: Selection of Lab Values at Follow-Up

The analysis windows are defined as follows:

Study Visit	Target Date (post procedure)	Protocol Defined Window (post procedure)	Expanded Analysis Window (post procedure)
1 Month	30	23-37	14-60
3 Months	90	76-104	61-135
6 Months	180	166-194	136-270
12 Months	360	330-390	271-540

Scenario 1: There are multiple ABPM raw data records with the same ABPM CPEVENT including SV2:

1. Starting with the most recent ABPM raw record, is there any Lab visit (SCHEDULED or UNSCHEDULED) where 'Lab follow up date' = 'ABPM start date'?
2. If yes, then use that Lab visit if it is in the expanded analysis window.
3. If no, then go to the previous ABPM raw record, and again look for any Lab visit (SCHEDULED or UNSCHEDULED) where 'Lab follow up date' = 'ABPM start date'. If yes, then use that Lab visit if it is in the expanded analysis window. In no, then go to the previous ABPM raw record...
4. Repeat for all ABPM raw records.

Scenario 2: There is only 1 ABPM raw data record for a given CPEVENT:

This algorithm only applies to the follow up measurements in the tables above. SV2 will still use site reported values. In case of multiple SV2 measurements, then take the latest one. Date of specimen collection will be used as lab follow up date.

1. Time to follow up will be calculated as (lab follow up – procedure date). Only SCHEDULED follow up data will be included in this analysis.
2. All follow up measurements <14 days post procedure will not be included in the follow up analysis unless otherwise specified.
3. The remaining measurements will be categorized per windows defined above. In case of multiple qualifying measurements, first take the one closest to the target follow up date, then take the latest one.

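### The SAP's one safety-rate rule, built on CEC-adjudicated events and last contact, does not fit the creatinine endpoint that the SAP exempts from adjudication

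*SAP*

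**What the plan says.** SAP 7.7.1 includes the creatinine rise in its list of safety endpoints and marks it "from SV2 (not CEC adjudicated". The paragraph after the list repeats the exemption: creatinine is the one endpoint that does not go to the CEC.

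The same paragraph then introduces a single rule: "The following algorithm will be used to evaluate the safety event rates". No endpoint is carved out.

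- Denominator: "The denominator will include all subjects who either had a CEC adjudicated event prior to the time of interest", or whose last contact falls after the lower limit of the visit window (day 166 for the 6-month rate).
- Numerator: "The numerator will include all subjects who had CEC adjudicated events up to the time of interest", with day 180 given as the example for 6 months.

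Protocol 13.5 states the opposite on adjudication, without exception: "All the safety endpoints will be adjudicated by the clinical events committee (CEC". SAP 7.10 records no change to the planned analysis.

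Two other places bear on creatinine. Protocol 9.1.8 asks for a second draw after a rise of more than 50%, recorded on an unscheduled-visit form: "The additional blood draw must be taken at least 21 days from the date of the event noted above". SAP Appendix V assigns laboratory values to visits. Where a visit has a single ABPM record (scenario 2), "Only SCHEDULED follow up data will be included in this analysis".

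**The concern.** An endpoint that is never adjudicated cannot enter a numerator made only of adjudicated events. The denominator has a matching problem: it asks whether the subject was contacted, not whether creatinine was measured. Appendix V does not fill the gap, because it selects values by visit window and defines no event, numerator or denominator.

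Loss of renal function is an obvious safety question for an ablation procedure in the renal arteries. As written, the plan either yields a rate that says nothing about the laboratory data, or leaves the event definition, the cut-off and the evaluable set to be chosen once the data are visible.

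**Working it through.** **1. The SAP's own figure.** Lower window limit for 6 months: 180 − 14 = 166, as stated. The upper limit is 180 + 14 = 194. The same arithmetic gives the other protocol windows in Appendix V: 30 ± 7 = 23 to 37, 90 ± 14 = 76 to 104, 360 ± 30 = 330 to 390.

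**2. Literal reading.** Numerator = subjects with a CEC-adjudicated creatinine event = 0, since none is adjudicated. With 50 treated subjects (the planned number) all contacted after day 166, the rate is 0/50 = 0% for any number of rises.

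**3. Loose reading, denominator.** Now let a laboratory rise stand in for an adjudicated event. The denominator is still driven by last contact. A subject can be contacted after day 166 without a creatinine value:

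- The schedule for escape subjects (Protocol Table 2, repeated as Table 4) has rows for office BP, imaging, mortality, and medication and event review, but none for blood tests.
- Protocol 9.1.6 lists laboratory tests among the assessments that cannot be completed at a virtual or phone visit.
- SAP 7.3 imputes nothing.

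Such subjects are counted as event-free. The documents give neither event counts nor missing-value counts, so both are assumed here:

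| Events | No value | Literal | Loose | Evaluable only |
|---|---|---|---|---|
| 1 | 5 | 0/50 = 0% | 1/50 = 2.0% | 1/45 = 2.2% |
| 1 | 10 | 0/50 = 0% | 1/50 = 2.0% | 1/40 = 2.5% |
| 3 | 5 | 0/50 = 0% | 3/50 = 6.0% | 3/45 = 6.7% |
| 3 | 10 | 0/50 = 0% | 3/50 = 6.0% | 3/40 = 7.5% |
| 5 | 10 | 0/50 = 0% | 5/50 = 10.0% | 5/40 = 12.5% |

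**4. Loose reading, cut-off.** The numerator stops at day 180, but a 6-month draw is on time from day 166 to day 194. That window has 194 − 166 + 1 = 29 days, and 194 − 180 = 14 of them (days 181 to 194) fall after the cut-off. A subject whose rise is first seen on day 185 is in the 6-month denominator by contact and missing from the numerator. The SAP gives day 180 only as an example. If the target day is the cut-off at every visit, the 12-month rate loses draws on days 361 to 390, with no later rate to pick them up.

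**5. Which draws are used.** Suppose Appendix V supplies the values.

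- Rise first seen at a scheduled visit from day 14 on, in the analysis window and selected for that visit, with the confirmatory draw on an unscheduled form: the index value stays and the event is kept. The endpoint, as defined in Protocol 4.2.2 and SAP 7.7.1, needs no confirmation.
- Rise first seen at an unscheduled draw: missed under scenario 2. Scenario 1 admits an unscheduled value only if its date equals the start date of an ABPM recording at a visit with several recordings.
- Draws before day 14, which include the discharge panel: left out unless otherwise specified.

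**6. Could it matter in a study this small?** The chance of at least one event among 50 subjects is 1 − (1 − p)^50. For assumed true rates p of 1%, 2% and 5% this is 39%, 64% and 92%.

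**The case against.** The strongest reply is that the exemption stands directly before the algorithm. A rule worded in terms of adjudicated events can then be read as covering adjudicated endpoints only, with creatinine left to the laboratory data. On that reading the report would not show an automatic 0%. This is fair: a reader might infer that the study will certainly report 0%, and the documents do not support that, because the zero depends on literal wording. But the alternative is nowhere written down, and the denominator and cut-off problems remain if the stated algorithm is merely adapted.

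A reader might also infer that leaving out the confirmatory draw of Protocol 9.1.8 deletes events. It does not, for the reason in step 5 of the working.

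Nor would renal harm be wholly hidden. Protocol 9.1.8 makes a confirmed rise a reportable adverse event, all adverse events are collected through 6 months, and a doubling of creatinine is an example under the adjudicated embolic-event definition. These routes are narrower than the endpoint. The first needs confirmation, only serious events are collected after 6 months, and the last is a different endpoint.

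Missing values are partly guarded against. The chemistry panel is scheduled at 1, 3, 6 and 12 months. Protocol 9.1.6 sends remote subjects to a local laboratory where possible and asks for missed data at the next in-person visit. Protocol 9.1.9 urges a panel before an escape subject restarts medication. After that, the escape schedule itself remains without blood tests.

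Finally, the study is unpowered and SAP 7.7.1 plans only counts and percentages for safety. It would be wrong to argue from an upper confidence bound on zero events, since no such bound is planned.

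**Conclusion.** The point holds as a defect in the stated rule. SAP 7.7.1 gives creatinine no workable numerator or denominator. The literal reading returns zero whatever the laboratory shows. The loose reading counts unmeasured subjects as event-free and drops valid 6-month draws on days 181 to 194. Appendix V scenario 2 adds a smaller loss, of rises first seen at an unscheduled draw. Protocol 13.5 and SAP 7.7.1 contradict each other on adjudication whichever reading is taken.

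The size of the effect is unknown, because the documents give no event rate and no count of missing laboratory values. The percentages in the table rest on assumed counts. The literal zero, the dropped days and the mismatch between contact and measurement do not. The endpoint is one descriptive safety rate without a comparator, so the consequence is a misleading renal safety figure and not a wrong efficacy conclusion.

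**What to change.** State in SAP 7.7.1 that the CEC algorithm applies to adjudicated endpoints only, and add a laboratory-based rule for creatinine:

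- **Numerator:** subjects with creatinine above 1.5 × the SV2 value at any scheduled or unscheduled post-procedure draw, up to the upper limit of that visit's protocol window (day 194 for 6 months). Show separately those confirmed under Protocol 9.1.8.
- **Denominator:** subjects with an SV2 creatinine who either had such an event or have a creatinine value in that visit's window. The numerator is then always contained in the denominator, including when a subject has an early rise and no later draw.
- **Report** the number of subjects not evaluable at each time point.

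Say that Appendix V's limits to scheduled draws and to day 14 onward do not apply to this endpoint. Reconcile Protocol 13.5 with the SAP on whether creatinine is adjudicated.

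The cost is one SAP paragraph and an alignment of the protocol text, with no new data collection. The rate may look slightly less favourable: more draws can yield an event, and subjects without a value no longer count as event-free.
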